#### **Added value compared to current knowledge/state of the art initiatives**

Vitamin D levels may have a protective effect on malignant melanoma outcome, as suggested by a reported association of higher 25(OH)D3 serum levels at diagnosis with lower Breslow thickness at diagnosis. Increased 25(OH)D3 serum levels at diagnosis were also independently protective of relapse and death (Newton Bishop, 2009). In the present proposal, we expand these investigations on the potential protective effect of vitamin D on melanoma outcome in a more comprehensive way, because of the following reasons:

1. We will test the protective effect of vitamin D supplementation to melanoma patients (in a placebo controlled and double blind way) against relapse (primary endpoint).
2. We will also immunohistochemically assess the expression of the Vitamin D Receptor (VDR) expression in the primary tumor, and investigate whether VDR immunoreactivity in the primary tumor correlates with relapse (primary endpoint) and melanoma stage at diagnosis. (secondary endpoint)
3. We will monitor increases in vitamin D levels after supplementation (secondary endpoint). This will allow us to assess whether every patient is characterized by the same increase in vitamin D, or whether serum levels following intake depends on genetic variability. Furthermore, this will allow us to monitor compliance to the supplementation.
4. We will correlate vitamin D levels at diagnosis with melanoma site (secondary endpoint) and subtype (secondary endpoint).

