### **3.2. Justification of study design**

A previous study has demonstrated the association of higher 25-hydroxyvitamin D3 serum levels with lower Breslow thickness of the tumor at diagnosis (Newton-Bishop, 2009), suggesting a protective effect of higher vitamin D levels on disease progression of cutaneous malignant melanoma.

To further proof the protective effect of Vitamin D supplementation on melanoma disease progression, this study will give high dose vitamin D supplementation to the melanoma patients after surgery of the primary tumor ( which is the current best standard of care), in a placebo controlled and double blind way. The effect of high dose vitamin D supplementation in double blind placebo controlled way will be primarily tested on relapse free survival.

Patients will be randomly assigned in a 1:1 ratio to receive a monthly oral dose of 100 000 IU of vitamin D (1ml of D-Cure) or placebo (1 ml of olive oil). A block randomization method stratified on time of diagnosis (newly diagnosed, 0-6 months or 6-12 months before start of the study) will be used to overcome seasonal influences on baseline characteristics.

We will also assess the expression of the Vitamin D Receptor (VDR) expression in the primary tumor. A blood sample will be taken for DNA analysis (genetic variability in the vitamin D pathway). We will check 25(OH)D3 serum levels both at diagnosis, and every 6 months until the end of the study. If the level of 25(OH)D3 serum is above 80 ng/ml, study drug will be interrupted and during drug free interval the 25(OH)D3 serum levels will be checked every 3 months. When serum 25(OH)D3 falls below 50 ng/ml, study drug is restarted

The patient cohort will exist of 3 subgroups (patients diagnosed within 6 or 12 months before start of the study and newly diagnosed patients). Inclusion of previously diagnosed patients will allow us to assess whether delayed supplementation has a similar effect on the relapse free survival rate as immediate supplementation after surgery of the tumor.

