#### 4.3.4. Clinical laboratory

Blood sampling and sample analysis is performed at the clinical centre. The local investigator is responsible for proper judgment of abnormal blood test results, and is responsible to appropriate patient care following clinically relevant pathological results. Please refer to section 6.4.4 to determine whether an abnormal laboratory value may constitute an adverse event.

The following analysis is to be obtained:

Screening and end of study:

- Hematology: hemoglobin, hematocrit, WBC count with differential, RBC count and platelet count
- Biochemistry and enzymes: serum creatinine, serum calcium, serum phosphate, AF, ALT, gamma GT, LDH

Randomisation (Day 0):

- Baseline serum vitamin D level.
- Bloodsample for DNA analysis

Every 3 months:

- serum calcium
- serum phosphorus
- 25(OH)D3 serum levels, in case of drug interruption when serum 25(OH)D3 levels are > 80 ng/ml

Every 6 months:

- 25(OH)D3 serum levels
- WBC plus differential

End of study: 24 hrs urine calcium

SNP analysis will be performed by the laboratory of [name], VIB

Peripheral blood from study participants will be sampled in K2EDTA tubes.

The samples are coded and only then transferred to VIB. So VIB only has coded information from the patients. Subsequently, tubes will be transferred to the Vesalius Research Center (Leuven) and genomic DNA will be extracted by a standard salting out method and stored at -80 °C until further analysis. Genetic variants affecting VD levels will be genotyped in a blinded manner using iPLEX technology on a MALDI-TOF based MassARRAY Compact Analyser (Sequenom Inc., CA, USA). The Sequenom's iPLEX technology efficiently multiplexes up to 32 different SNP's in one PCR reaction, thereby providing rapid and accurate SNP genotypes at an affordable price. Only samples for which ≥ 80% SNPs have succeeded will be considered for further analysis. SNPs with a call rate < 98% will be re-designed and genotyped again to reach success rates close to 100%. At least 5% of the samples will be genotyped in duplicate, to prove accuracy of the genotyping protocol. We expect that approximately 2 Sequenom assays will have to be applied on the DNA of participating individuals to cover all 19 SNPs. Multiple Single Nucleotide Polymorphisms (SNPs) have been reported to affect VD signaling.

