### 5.1.5. Use, accountability and destruction

Pharmacists of the University Hospitals Leuven, who are independent from the clinical study team, will randomly assign participants by using a computer-generated randomization list and prepare the study medication. A diary will be given to the patient for dates when to take the medication (numbered syringes) on a monthly base, at a dose of 100 000 IU (1 ml of D-cure® suspension in ) or 1 ml of placebo (olive oil). Vitamin D and placebo are prepared by Laboratoires SMB NV in oral ampoules , identical in taste and appearance. Oral ampoules are numbered according the randomization schedule. At each visit 3 numbered ampoules are given to the patient, Patient will take empty ampoules back to the control visit (every 3 months). Number of ampoules and date the Vitamin D/placebo is taken are registered. Subsequently empty ampoules are destroyed

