### **7.2. Statistical Methods**

The primary analysis is an intent-to treat analysis of all randomised patients. Patients will be analysed according to the treatment group to which they were randomised, irrespective of which study drug was given or if any study drug was received. Additional populations like a per protocol population may be defined in the statistical analysis plan

The difference in relapse-free survival will be compared between the two treatment groups by means of a Cox proportional hazards model stratified for time since diagnosis (3 strata: 0, 6 or 12 months ago). It will be verified whether the treatment effect is stratum dependent. If so, the strata will be analysed separately. Furthermore, using a Cox proportional hazards model it will be investigated whether the potential treatment effect is different for VDR immunoreactivity and genetic variability in the Vitamin D pathway. A correction for other baseline covariates like gender, age and

baseline Vitamin D level will be performed as sensitivity analyses. No interim analysis for efficacy is foreseen. Potential subgroups analysis like for instance calcium serum levels will be defined in the statistical analysis plan

The evolution in 25(OH)D3 levels in function of genetic variability in the Vitamin D pathway will be analysed by a linear mixed model. Sensitivity analyses will include patient's compliance, seasonal effects and patient's baseline characteristics like age and gender.

In order to examine the effect of the actual 25(OH)D3 levels rather than just supplementation, the evolution of 25(OH)D3 levels and relapse-free survival will be jointly modelled.

The potential correlation between VDR immunoreactivity and stage at diagnosis will be assessed by means of a Kruskal Wallice test.

The potential correlation between vitamin D levels at diagnosis with melanoma site and melanoma subtype will be assessed by means of an analysis of variance. This analysis can only be performed for newly diagnosed patients because vitamin D levels at diagnosis will not be available for patients who had their diagnosis 6 or 12 months ago.

Full details of the statistical analyses will be described in a statistical analysis plan which will be finalized before database lock.

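### The 25(OH)D3 draw is not fixed relative to the monthly ampoule, and section 7.2 names no time-since-dose term although intake dates are registered

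*Combined protocol and SAP*

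**What the plan says.** Protocol sections 3.2 and 5.1.5 set one oral 100 000 IU ampoule, or 1 ml of olive oil, per month. On sampling, section 3.2 says "We will check 25(OH)D3 serum levels both at diagnosis, and every 6 months until the end of the study". Table 1 in section 4.1 adds a draw at end of study or at progression/relapse. Section 4.3.4 repeats the 6-monthly schedule; its only 3-monthly draws are "25(OH)D3 serum levels, in case of drug interruption when serum 25(OH)D3 levels are > 80 ng/ml". None of these places gives a draw time relative to the ampoule, or a visit window.

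Section 5.1.5 records what is needed to reconstruct timing: "Number of ampoules and date the Vitamin D/placebo is taken are registered". It also links dosing loosely to visits: "At each visit 3 numbered ampoules are given to the patient".

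Section 7.2 gives the analysis: "The evolution in 25(OH)D3 levels in function of genetic variability in the Vitamin D pathway will be analysed by a linear mixed model". Its sensitivity analyses cover compliance, season and baseline characteristics such as age and gender. The same section plans a joint model of 25(OH)D3 and relapse-free survival. It leaves full details to an analysis plan to be finalised before database lock, which is not part of the text reviewed.

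The list of added value in section 1.1 uses the follow-up levels to ask whether response depends on genotype, and continues: "Furthermore, this will allow us to monitor compliance to the supplementation".

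**The concern.** After a monthly bolus the serum level rises and then falls until the next dose. A fully compliant patient can be drawn on day 2 or on day 29 of the cycle and give different readings with no difference in response or adherence. If the models do not account for this, cycle position goes into the residual. There it can look like variable response or poor compliance, and it costs some precision in the genotype analysis.

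The joint model raises a second issue. Scheduled visits tend to fall when the third ampoule of a set is nearly a month old. A visit prompted by a suspected relapse need not. If such draws enter the longitudinal part, the level at the event would sit systematically higher in the cycle than the scheduled levels before it. That is a shift in the mean, not only noise.

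Of the four secondary endpoints in section 2.2, the 25(OH)D3 series is the only one measured after randomisation, so its measurement deserves this care.

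**Working it through.** **Inputs from the protocol**
- Expected rise: 70 nmol/L, described as 80% of the effect in the cited COPD trial (section 7.1).
- Conversion: 20 ng/ml = 50 nmol/L (section 1.1), so 1 ng/ml = 2.5 nmol/L.
- Dosing interval: one month, taken as T = 30.4 days.
- Extra D-Cure of 25 000 IU/month at low levels, with no restriction by arm (section 6.1.2).

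**Assumptions, not in the documents**
- Half-life of 21 to 60 days; first-order decay with immediate conversion.
- Draw windows as stated below.
- Other within-patient SD of 5 ng/ml; between-patient SD of 10 ng/ml.

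**Step 1. The protocol's own figure.** 70/0.8 = 87.5 nmol/L, and 87.5/2.5 = 35 ng/ml. This agrees with section 1.1, where levels go from below 20 to 50 ng/ml, a rise of more than 30. The planned rise is 70/2.5 = 28 ng/ml. The protocol states no target precision for the 25(OH)D3 models, so there is none to reproduce.

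**Step 2. Steady-state cycle with mean rise D = 28.** With k = ln 2 / half-life, peak = D·k·T / (1 − exp(−kT)) and trough = peak·exp(−kT). For a half-life of 30 days: k = 0.0231, kT = 0.702, peak = 28 × 0.702 / (1 − 0.495) = 39.0 and trough = 19.3.

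| Half-life (days) | Peak | Trough | Swing | SD, random timing | SD, within 7 days of cycle end |
|---|---|---|---|---|---|
| 21 | 44.4 | 16.3 | 28.1 | 8.0 | 2.2 |
| 30 | 39.0 | 19.3 | 19.7 | 5.7 | 1.8 |
| 45 | 35.1 | 22.0 | 13.1 | 3.8 | 1.4 |
| 60 | 33.2 | 23.4 | 9.8 | 2.8 | 1.1 |

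Levels are rises in ng/ml. Random timing is an upper bound: dispensing pulls scheduled visits towards cycle end, and conversion in the liver flattens the peak. The last column takes draws evenly spread over T ± 7 days with the next ampoule not yet taken.

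**Step 3. A mixed case.** Suppose 80% of draws are within 7 days of cycle end and 20% are random (assumed). The variance is 0.8 × window variance + 0.2 × random variance + 0.8 × 0.2 × (difference in means)². For a half-life of 30 days: 0.8 × 1.81² + 0.2 × 5.65² + 0.16 × 8.6² = 2.6 + 6.4 + 11.8 = 20.8, so the SD is 4.6. Over half-lives of 21, 30, 45 and 60 days it is 6.2, 4.6, 3.2 and 2.4 ng/ml. A minority of off-cycle draws restores much of the variation.

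**Step 4. Relapse draws.** A draw at a random cycle point averages 28; one at cycle end averages the trough. The difference is 28 − 16.3 = 11.7 at 21 days and 28 − 23.4 = 4.6 at 60 days, so about 5 to 12 ng/ml in patients on vitamin D.

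**Step 5. Placebo arm.** If extra D-Cure is taken monthly and its effect is proportional to dose, its share is 25 000/100 000 = one quarter. The random-timing SD is then 8.0/4 = 2.0 down to 2.8/4 = 0.7 ng/ml, in supplemented patients only.

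**Step 6. Effect on the models.**
- Within-patient variance, for half-lives of 30 to 60 days: 1.8²/25 = 13% and 1.1²/25 = 5% more with the 7-day window.
- Standard error of a between-patient genotype contrast with 4 samples each: the base variance is 100 + 25/4 = 106.25. A timing SD of 6 gives 100 + 61/4 = 115.25, and √(115.25/106.25) = 1.04. A timing SD of 1.8 gives 107.06, and √(107.06/106.25) = 1.004. The loss is therefore about 0.4% to 4%.

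**The case against.** The best counter-argument is that this is a small matter in secondary analyses. Timing unrelated to genotype adds variance, not bias. Averaged over visits it widens a genotype contrast by only a few per cent. A joint model already separates residual error from the underlying trajectory. The three-ampoule dispensing keeps most scheduled draws near cycle end, and the analysis plan may yet add the term. Most of this stands and sets the weight of the point. It does not answer the possible mean shift in relapse draws, or the fact that a common residual variance would be wrong if the noise differs by arm. A later analysis plan also cannot recover the same-day order of ampoule and draw from dates alone.

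Three stronger readings are tempting, and the documents do not support them:
- **That only the vitamin D arm is affected.** Section 6.1.2 gives extra D-Cure at low levels without regard to arm, so some placebo patients also have a dosing cycle.
- **That the models ignore the intake dates.** Section 7.2 only does not say that they use them. The compliance analysis may draw on the same records, and details are deferred. Compliance is still not a substitute for days since last dose.
- **That within-patient variance more than doubles.** That needs close to random timing (5.7²/25 = 130% more at a 30-day half-life) or a sizeable share of off-cycle draws combined with a short half-life. Neither is shown.

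**Conclusion.** The point holds as a minor improvement. The draw is not fixed relative to the ampoule, and no time-since-dose term is named although the data for one are collected. The timing variation is larger in the vitamin D arm without being confined to it. Its SD is about 1.1 to 2.2 ng/ml if all draws fall within 7 days of cycle end, with 2.8 to 8.0 ng/ml as the upper bound. The consequence most worth guarding against is the possible 5 to 12 ng/ml excess in off-cycle relapse draws. It applies only to relapses found outside the regular visits, and only if those draws enter the joint model. Only the 28 ng/ml rise comes from the protocol; the half-life, windows and SDs are assumed. The primary intention-to-treat Cox analysis does not use the levels and is untouched.

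**What to change.** In section 4.3.4, state that the 25(OH)D3 sample is taken before any ampoule that day, and that the date of the last intake is recorded with it.

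In section 7.2 or the analysis plan, add days since last vitamin D intake to the 25(OH)D3 mixed model and to the longitudinal part of the joint model, at least as a sensitivity analysis. Count both study drug and any extra D-Cure. Include an arm interaction, or allow an arm-specific residual variance. Flag periods of drug interruption for levels above 80 ng/ml separately; otherwise days since last intake runs to months, and long washout is mixed with position in the monthly cycle.

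The cost is a line in the laboratory section, a few model terms and a rule for missing intake dates. Dosing does not change.

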
**Vitamin D status: current knowledge**

There are 3 sources of vitamin D: endogenous production in skin upon absorption of ultraviolet (UV) B (290-315 nm) radiation, vitamin D in foods and finally dietary supplements. Since a standard western diet contains only very few food components, which contain vitamin D (fatty fish and liver extracts) our most important source of vitamin D is endogenous conversion of 7-dehydrocholesterol (7-DHC) to previtamin D3 by UVB, which isomerizes to vitamin D3 by thermal energy. However, this vitamin D synthesis is only reliably available year-round at latitudes between 40 ° north and 40 ° south, indicating that in our regions the required levels of UVB are low or non-existent for a significant proportion of the year. Data indicate that indeed insufficient vitamin D levels are widespread both in the American and European population (Holick 2006; Lee 2009; Adams 2010,) especially in wintertime (Rhodes 2010).

Vitamin D (from the food, via supplements or produced by UVB in the skin) is biologically inert and the biological effect of vitamin D results only as a consequence of its sequential metabolism in the liver into 25-hydroxy-vitamin D3 (25(OH)D3) and then in the kidney into the steroid hormone, 1alpha,25-dihydroxyvitamin D3 (1,25(OH)2D3). The classical signaling pathway of 1,25(OH)2D3 employs the vitamin D receptor (VDR), which is a transcription factor for 1,25(OH)2D3 target genes, including the cyclin dependent kinase inhibitors, p21 and p27.

Vitamin D receptor (VDR) is believed to be located in the nucleus prior to activation by 25(OH)2D3, which dissociates from the serum vitamin D-binding protein, enters the cell by diffusion and binds the VDR. Ligand binding produces conformational changes, resulting in dimerization, necessary for high affinity interaction with target gene promoter at the vitamin D response element (Osborne, 2002).

The gene encoding VDR maps to the chromosomal region 12q13 and contains numerous common variants, that are hypothesized to influence the function and or expression of VDR (Egan 2009).

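### The ANOVA of 25(OH)D3 by melanoma site and subtype has no season term, and the mixed model treats season only as a sensitivity analysis; sampling date belongs in both main models

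*Combined protocol and SAP*

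**What the plan says.** Section 7.2 plans three analyses with 25(OH)D3 as an outcome or a modelled course.

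- **Site and subtype.** "vitamin D levels at diagnosis with melanoma site and melanoma subtype will be assessed by means of an analysis of variance". The next sentence limits the data: "This analysis can only be performed for newly diagnosed patients because vitamin D levels at diagnosis will not be available" for patients diagnosed 6 or 12 months earlier. No covariate is named.
- **Genotype.** "The evolution in 25(OH)D3 levels in function of genetic variability in the Vitamin D pathway will be analysed by a linear mixed model". The text then adds: "Sensitivity analyses will include patient's compliance, seasonal effects and patient's baseline characteristics like age and gender".
- **Joint model.** "the evolution of 25(OH)D3 levels and relapse-free survival will be jointly modelled". Season is not mentioned.

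Section 1.1, under the heading on vitamin D status, gives skin synthesis under UVB as the most important source of vitamin D and says that "in our regions the required levels of UVB are low or non-existent for a significant proportion of the year". It adds that insufficiency is widespread, and more so in winter. In section 3.2, block randomisation stratified on time of diagnosis "will be used to overcome seasonal influences on baseline characteristics". Section 7.2 leaves full detail to a statistical analysis plan to be finalised before database lock.

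**The concern.** The protocol names season as a driver of the very quantity being modelled, but none of the main models described contains it. This has two possible consequences.

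1. **Precision.** Seasonal variation that is left out goes into the residual. In an ANOVA with one sample per patient, nothing cancels it.
2. **Confounding of site and subtype.** Patients are not randomised to a melanoma site or subtype. If one group happens to be sampled more often in the sunny months, the seasonal difference is read as a difference in vitamin D between the groups.

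The stratification in section 3.2 does not help here. It acts on treatment allocation, so it can balance only the arms. It is also based on time since diagnosis, which is not calendar month.

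**Working it through.** **Inputs.** The documents give no seasonal amplitude, SD, number of newly diagnosed patients, or power for any 25(OH)D3 analysis. Their only power statement (90% for a hazard ratio of 0.40 with 500 patients) concerns relapse-free survival and does not bear on this point, so there is no plan figure to reproduce. Assumed here: an annual sinusoid with amplitude A = 10-20 nmol/L (half of peak-to-trough) and within-season SD s = 20-25 nmol/L.

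**Step 1: share of variance in the ANOVA.** With sampling spread over the year, a sinusoid has variance A²/2. Season's share is (A²/2)/(s² + A²/2). The number of patients needed without adjustment, relative to with it, is 1 + (A²/2)/s².

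| A (nmol/L) | s (nmol/L) | A²/2 | Share of variance | Worth in extra patients |
|---|---|---|---|---|
| 10 | 25 | 50 | 50/675 = 7.4% | 50/625 = 8% |
| 15 | 25 | 112.5 | 112.5/737.5 = 15.3% | 112.5/625 = 18% |
| 20 | 25 | 200 | 200/825 = 24.2% | 200/625 = 32% |
| 20 | 20 | 200 | 200/600 = 33.3% | 200/400 = 50% |

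In terms of power, a contrast with 80% power when adjusted has power Φ((1.96 + 0.84)/√(1 + gain) − 1.96) when unadjusted (two-sided 5%, assumed). That is about 77% at a gain of 8% and about 63% at a gain of 50%.

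**Step 2: bias in a site or subtype contrast.** The sunny half-year has mean +2A/π and the dark half −2A/π, a difference of 4A/π. If two groups differ by d in the share sampled in the sunny half, the spurious difference is d × 4A/π.

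| d | A = 10 | A = 15 | A = 20 |
|---|---|---|---|
| 0 | 0 | 0 | 0 |
| 0.10 | 1.3 | 1.9 | 2.5 |
| 0.20 | 2.5 | 3.8 | 5.1 |

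(nmol/L; for example 0.20 × 4 × 15/π = 3.8.)

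**Step 3: simulation.** 4,000 data sets of 150 patients, one sample each, A = 8 and s = 10 ng/ml. These are 20 and 25 nmol/L at the protocol's own equivalence of 10 ng/ml to 25 nmol/L. No true group difference was built in.

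- Two site groups with 60% and 40% sunny-half sampling: unadjusted bias 2.09 ng/ml and type I error 19%. With sine and cosine of date in the model, bias 0.03 ng/ml and type I error 4.8%.
- Genotype drawn independently of date: bias 0.02 ng/ml and type I error 5.2% without adjustment. Only the standard error changes, from 1.40 unadjusted to 1.22 adjusted.

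**Step 4: why the Step 1 gain does not carry over to the mixed model.** The protocol samples every 6 months. Two samples half a year apart sit at opposite phases of an annual cycle, since sin(t) + sin(t + π) = 0. Season therefore partly cancels in a patient's mean, although it still makes the individual course alternate and adds residual variance. The net gain depends on visit numbers and the correlation structure, and it is not quantified here.

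**The case against.** **Season is already planned for the mixed model.** This is true, and both adjusted and unadjusted results would be produced either way. For that model the change is which result is the main one. The sentence on sensitivity analyses does not reach the ANOVA, though. It follows the mixed model directly and lists compliance, which has no meaning for a level taken at diagnosis.

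**Detail is deferred to a later plan.** This is a fair point, and that plan could still add season. But section 7.2 already gives season secondary status in one model and no role in the other, so this is a stated choice and not only a gap.

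**The confounding is hypothetical.** This stands. Nothing in the documents shows that sites or subtypes are sampled at different times of year, and the 20-point difference is an illustration. The honest range starts at zero.

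**Stronger readings that a reader might infer.**

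- That season also confounds genotype. The documents give no mechanism. Germline variants do not depend on the date of a blood draw, apart from chance or an indirect link through centre or ancestry.
- That stratifying on time since diagnosis leaves the arms unbalanced by season and so threatens the primary result. Section 3.2 concerns balance between randomised arms, and the primary comparison does not rest on 25(OH)D3.
- That age, sex and BMI should be added as well. No defect has been shown there. The background links some sites and subtypes to chronic photodamage, so adding age might change the question as well as remove noise.

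**Conclusion.** The point holds for the site and subtype ANOVA, and in a weaker form for the mixed model. That no main 25(OH)D3 model in section 7.2 contains season is certain from the text. The loss of precision in the ANOVA follows whenever season matters. Its size (7%-33% of variance, 8%-50% in equivalent patients) rests on the assumed amplitude and SD. The bias in site and subtype contrasts is conditional: zero with balanced sampling dates, 2.5-5.1 nmol/L at a 20-point imbalance, with the documents silent on which applies. For genotype the issue is precision alone, with no figure attached. These are secondary analyses, so the change is worth making but has no bearing on the trial's main conclusion.

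**What to change.** In the statistical analysis plan, before database lock:

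- Prespecify sine and cosine of the blood-sampling date (annual period) as fixed covariates in the main analysis of 25(OH)D3 at diagnosis by site and by subtype, so that the ANOVA becomes an ANCOVA.
- Put the same two terms in the main 25(OH)D3 mixed model.
- Keep the unadjusted versions of both as sensitivity analyses.
- Tabulate sampling month by site and by subtype, so that a reader can see whether any imbalance exists.

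Use the date of the draw itself: Table 1 schedules the first level at randomisation, whereas section 4.2 places it at diagnosis.

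The cost is two degrees of freedom per model and a few sentences. Every scheduled sample has a date, so no new data are needed. Calendar month as a factor would also work but uses eleven degrees of freedom.
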